10.2 Populations for Analyses

For purposes of analysis, the following populations are defined:

Population	Description
Enrolled	All participants who sign informed consent. This is the dataset for disposition.
Treated	All enrolled participants who received at least one dose of study drug. This is the dataset for safety evaluation.
Safety Lead-in participants	In Module A, the first 6 DLT-evaluable participants in Cohort 1 and the first 10 DLT-evaluable participants in Cohorts 2-5; in Module B, the first 10 DLT-evaluable participants.
Response-evaluable participants	All treated participants with measurable disease at a baseline tumor assessment (Source: CRF).
[REDACTED]	[REDACTED]
[REDACTED]	[REDACTED]

10.3 Statistical Analyses

The statistical analysis plan will be developed and finalized before database lock and will describe the selection of participants to be included in the analyses, and procedures for accounting for missing, unused, and spurious data. Below is a summary of planned statistical analyses of the primary and secondary endpoints.

10.3.1 Efficacy Analyses

The primary efficacy analyses will be performed on treated population for the final analysis. Details on censoring scheme on time-to-event endpoints such as OS, PFS, and DOR will be described in the SAP. Efficacy analysis will be performed by each cohort separately; however, treated participants in the safety lead-in period who meet the inclusion criteria for the corresponding cohort will also be included in the cohort analysis.

OS is defined as the time between the date of diagnosis and the date of death in Cohort 1 and the time between date of first dose and the date of death for Cohorts 2-5. A participant who has not died will be censored at the last known alive date. OS will be followed continuously while

participants are on study drug and every 3 months via in-person or phone contact during the survival follow-up phase of the study drug.

PFS is defined as the time from first dose to the date of the first documented tumor progression or death due to any cause. Participants who die without a reported prior progression will be considered to have progressed on the date of death. Participants who did not have disease progression or die will be censored at the date of last evaluable tumor assessment. Participants who did not have any on study tumor assessment and did not die will be censored at the first dose date. PFS will be determined by investigators based on RANO criteria. First tumor assessments will occur at week 6 and 12, and will be at every 8 weeks for the first year and then every 12 weeks thereafter until disease progression is documented.

ORR is defined as the number of participants whose BOR is confirmed CR or PR divided by all participants who are evaluable for response, ie have measurable disease at baseline. BOR is defined as the best response designation, as determined by investigators, recorded between the date of first dose and the date of objectively documented progression per RANO criteria or the date of subsequent therapy, whichever occurs first. All available response designations will contribute to the BOR assessment. For participants without documented progression or subsequent therapy, all available response designations will contribute to the BOR assessments.

DOR for a participant with a BOR of CR or PR, is defined as the time between the date of first response and the date of the first objectively documented tumor progression per RANO or death, whichever occurs first.

Endpoint	Statistical Analysis Methods
Primary	
Cohort A1 and B1: OS	For each cohort separately, OS curve will be estimated using the Kaplan-Meier (KM) method. The distribution of OS in all treated participants will be compared against the historical control of an exponential distribution with median OS 9 months (Cohen, Heideman, et al) using a one-sided one-sample log rank test when approximately 17 events have occurred or after each participant has been followed for at least 24 months. Median OS and the corresponding two-sided 80% confidence intervals using the log-log transformation will be computed.
Cohort A2 and B2: PFS	For each cohort separately, PFS curve will be estimated using the Kaplan-Meier (KM) method. The distribution of PFS in all treated participants will be compared against the historical control of an exponential distribution with median PFS 2.25 months (Hwang, et al) using a one-sided one-sample log rank test when each participant has been followed for at least 12 months. Median PFS and the corresponding two-sided 80% confidence intervals using the log-log transformation will be computed.
Cohort A3 and B3: PFS	For each cohort separately, PFS curve will be estimated using the Kaplan-Meier (KM) method. The distribution of PFS in all treated

Endpoint	Statistical Analysis Methods
	participants will be compared against the historical control of an exponential distribution with PFS(4) equal to .18 using a one-sided one-sample log rank test when either 15 events have occurred or each participant has been followed for at least 12 months. Median PFS and the corresponding two-sided 80% confidence intervals using the log-log transformation will be computed.
Cohort A4 and B4: PFS	For each cohort separately the distribution of PFS in all treated participants will be compared against the historical control of an exponential distribution with median PFS equal to 2.1 months using a one-sided one-sample log rank test when either 10 events have occurred or each participant has been followed for at least 12 months.
Cohort A5 and B5: PFS	For each cohort separately individual PFS will be listed by tumor type after each participant reaches 12 months follow-up. PFS curve will be estimated using the Kaplan-Meier (KM) method for all tumor types (pooled) and selected individual tumor types, if there is enough data.
Secondary	
Cohort A1 and B1: PFS, OS(12)	Cohorts A1 and B1: PFS is estimated by Kaplan-Meier method and the corresponding 95% CI for median OS will be calculated via Brookmeyer and Crowley methodology using log-log transformation. OS(12) will be estimated using the Kaplan-Meier (KM) method. The corresponding 95% confidence interval for median OS will be calculated via Brookmeyer and Crowley methodology using log-log transformation and corresponding 95% confidence interval for OS(12) will be derived based on Greenwood formula. All secondary endpoints will be analyzed at the time of the primary analysis.
Cohort A2 and B2: PFS(6), OS, OS(12) Cohort A3 and B3: PFS(6), OS, OS(12) Cohort A4 and B4: PFS(6), OS, OS(12)	Cohorts A2, A3, A4, B2, B3, B4 Secondary statistics analysis for other cohorts A2, A3, and A4, B2, B3, and B4 is the same as for Cohort A1 and B1 (except timepoint for OS(r) and PFS(r) may differ.
Cohort A5 and B5: PFS(12), OS	Cohorts A5, B5: OS will be listed. OS curve will be computed using Kaplan-Meier method for pooled indications and selected individual indications. The corresponding 95% confidence interval for median OS will be calculated via Brookmeyer and Crowley methodology using log-log transformation and corresponding 95% confidence interval for PFS(12) will be derived

Endpoint	Statistical Analysis Methods
	based on Greenwood formula.

[REDACTED]
 
[REDACTED]
	
[REDACTED]
 
[REDACTED]

[REDACTED]
	
[REDACTED]

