Cohorts A2 and B2: Sample sizes of 15 participants for each of the Cohorts A2 and B2 in HGG is based on an historical PFS(6) of 18%, one-year accrual, one year follow-up, a target PFS(6) of 38% providing 80% power using a one-sided Type 1 error of 10%, assuming an exponential distribution.

Cohort A3 and B3: Sample sizes of 15 participants for each of the cohorts is based on comparison of PFS against an historical control of PFS rate at 4 months of .18, assuming 80% power, 1-sided alpha of 10%, target PFS rate at 4 months of .38, and a one-sample log rank test. All distributions are assumed to be exponential; assume 12 months for accrual and 12 months follow-up.

Cohort A4 and B4: Sample sizes of 10 participants for each of the cohorts is based on comparison of PFS against an historical control of median PFS of 2.1 months, assuming 80% power, 1-sided alpha of 10%, target median PFS of 4.4 months, and a one-sample log rank test. All distributions are assumed to be exponential; assume 12 months for accrual and 12 months follow-up.

Cohort A5 and B5: Sample sizes of 18 participants for each of the Cohorts A5 and B5 is not based on statistical considerations as these cohorts contain various tumor types. However, if the disease control rate at 12 months is 30%, 18 patients provide 21% precision for the estimate.

[figure not shown]
Treatment Arms and Duration:

Study treatment:

Study Drug for CA209908		
Medication	Potency	IP/Non-IP
Nivolumab (BMS-936558-01) Solution for Injection ^a	100 mg (10 mg/mL)	IP
Ipilimumab (BMS-734016) Solution for Injection	200 mg (5 mg/mL)	IP

^a May be labeled as either “BMS-936558-01” or “Nivolumab”

Figure 1-1: Overall Study Design Schematic

Notes:

- Cohorts are indicated by tumor type; Study Treatments are indicated as A = nivolumab and B = nivolumab + ipilimumab
- Safety is evaluated *across* cohorts (indicated as “lead-in”), prior to expansion
- Efficacy is evaluated *by* cohort (indicated as Expansion), including lead-in population
- Module B opens, by cohort, when corresponding Module A is completed or upon decision of Steering Committee

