10. STATISTICAL CONSIDERATIONS

10.1 Sample Size Determination

[REDACTED]

[REDACTED]

[REDACTED]

[REDACTED]

[REDACTED]

By applying the above methodology, the intended target number of participants (N) for cohort 1-4 are obtained as follows:

Cohort 1: 22 participants are required (17 events) for each cohort. This assumes 80% power with a one-sided Type 1 error of 10%, a historical median OS of 9 months (██████████), 1-year accrual, 2-year follow-up, and a target effect size of median OS 15 months.

Cohort 2: 15 participants are required for each cohort. This assumes 80% power with a one-sided Type 1 error of 10%, a historical PFS(6) of 18% (██████████), one-year accrual, one-year follow-up, a target PFS(6) of 38%. An interim analysis based on PFS(6) for futility only will be conducted after at least 8 of the planned number of participants are enrolled with 6 months follow-up. In addition, all other available efficacy data will be evaluated in the futility analysis. The method is adapted according to ██████████. Details of the futility criteria and simulations will be contained in the Statistical Analysis Plan (SAP).

Cohort 3: 15 participants are required for each cohort. This assumes 80% power with a one-sided Type 1 error of 10%, 1-year accrual and 1-year follow-up, a historical median PFS(4) of 18% and a target PFS(4) of 38% (see ██████████, equivalent to PFS(6) of 23%). An interim analysis based on PFS(6) for futility only will be conducted after at least 8 of the planned number of participants are enrolled with 6 months follow-up. In addition all other available efficacy data will be evaluated in the futility analysis.

Cohort 4: 10 participants are required for each cohort. This assumes at least 80% power with a one-sided Type 1 error of 10%, a historical median PFS of 2.1 months (see etoposide arm of ██████████), 1-year accrual, 1-year follow-up, and a target median PFS of 4.4 months.

Cohort 5: 18 participants are required for each cohort. Sample sizes each of the expansion Cohorts A5 and B5 is not based on statistical considerations as these cohorts contain various tumor types. However, if the disease control rate at 12 months is 30%, 18 participants provide 21% precision for the estimate.

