7.5.2 Progression Free Survival

For all cohorts, progression free survival (PFS) is defined as the time from first dose to the date of the first documented tumor progression or death due to any cause. Participants who die without a reported prior progression will be considered to have progressed on the date of death. Participants who did not have disease progression or die will be censored at the date of last evaluable tumor assessment. Participants who did not have any on study tumor assessment and did not die will be censored at the first dose date. PFS will be determined by investigators based on RANO criteria. First tumor assessments will occur at week 6 and 12, and will be at every 8 weeks for the first year and then every 12 weeks thereafter until disease progression is documented

7.5.2.1 Progression Free Survival for Cohorts 1

As one of the secondary endpoints of Cohort 1, PFS is estimated by Kaplan-Meier method and the corresponding 95% CI for median PFS will be calculated via Brookmeyer and Crowley methodology using log-log transformation. It will be analyzed at the time of the primary analysis.

7.5.2.2 Progression Free Survival for Cohorts 2 to 4

As the primary efficacy endpoints of cohorts 2 to 4, PFS curve will be estimated using the Kaplan-Meier (KM) method. Median PFS and the corresponding two-sided 80% confidence intervals using the log-log transformation will be computed.

The distribution of PFS for cohort 2 will be compared against the historical control of an exponential distribution with median PFS 2.25 months [REDACTED] using a one-sided one-sample log rank test when each participant has been followed for at least 12 months.

The distribution of PFS for cohort 3 will be compared against the historical control of an exponential distribution with PFS(4) equal to .18 using a one-sided one-sample log rank test when either 15 events have occurred or each participant has been followed for at least 12 months.

The distribution of PFS for cohort 4 will be compared against the historical control of an exponential distribution with median PFS equal to 2.1 months using a one-sided one-sample log rank test when either 10 events have occurred or each participant has been followed for at least 12 months.

In addition, as one of the secondary endpoints, PFS rate at 6 months will be estimated using KM estimates on the PFS curve and its corresponding 95% confidence interval will be derived based on Greenwood formula.

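### Cohort 2 is sized against a historical PFS(6) of 18% but tested against an exponential with median 2.25 months, which is PFS(6) of 15.7% and an easier null to beat

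*Protocol*

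**What the plan says.** **Sizing.** The protocol synopsis says "Sample sizes of 15 participants for each of the Cohorts A2 and B2 in HGG is based on an historical PFS(6) of 18" per cent, with "one-year accrual, one year follow-up" and "a target PFS(6) of 38% providing 80% power using a one-sided Type 1 error of 10%, assuming an exponential distribution". Protocol 10.1 repeats "a historical PFS(6) of 18" per cent with the same target, error, power, accrual and follow-up, and SAP 5 carries the same figures.

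**Primary test.** In the efficacy table of Protocol 10.3.1, the PFS distribution for Cohorts A2 and B2 is "compared against the historical control of an exponential distribution with median PFS 2.25 months", "using a one-sided one-sample log rank test when each participant has been followed for at least 12 months". SAP 7.5.2.2 also names "an exponential distribution with median PFS 2.25 months" as the Cohort 2 control.

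**Other cohorts.** The sizing null and the test null agree in Cohort 1 (median OS 9 months), Cohort 3 (PFS(4) of 18%) and Cohort 4 (median PFS 2.1 months). Only Cohort 2 differs.

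**Interim.** Protocol 10.3.5 and SAP 7.5.4 apply a one-sample log-rank test to each simulated completed cohort. Futility may be declared if the predictive probability of success is below 20%. The null for that test is not named there.

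**The concern.** An exponential distribution has one parameter, so a six-month rate fixes the median and a median fixes the six-month rate. The plan gives one figure for sizing and another for testing, and they describe different exponentials. The test null has the higher hazard, so it is the poorer historical control and the easier one to beat.

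A treatment that only matches the 18% benchmark would then be declared better than history more often than the stated 10%. The stated error rate and power would also describe a test that neither document specifies. This is the primary efficacy decision for both A2 and B2. If the interim simulation uses the same null, predicted success rises and stopping for futility becomes less likely. Preliminary efficacy in recurrent HGG also bears on whether the steering committee recommends a newly diagnosed HGG cohort (Protocol 5.1.6.2).

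**Working it through.** **Inputs.** From the synopsis, Protocol 10.1 and SAP 5: n = 15 per module, null PFS(6) = 0.18, target PFS(6) = 0.38, one-sided alpha 0.10, power 0.80, accrual 12 months, follow-up 12 months. From Protocol 10.3.1 and SAP 7.5.2.2: test null exponential with median 2.25 months.

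**Step 1. Convert to hazards.** Hazard = −ln(PFS(6))/6; median = ln 2/hazard.

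| | Hazard per month | Median (months) | PFS(6) |
|---|---|---|---|
| Sizing null | −ln(0.18)/6 = 0.2858 | 2.43 | 18% |
| Test null | ln 2/2.25 = 0.3081 | 2.25 | exp(−6 × 0.3081) = 15.7% |
| Target | −ln(0.38)/6 = 0.1613 | 4.30 | 38% |

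The test null hazard is 0.3081/0.2858 = 1.078 times the sizing null hazard.

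**Step 2. Rounding.** PFS(6) from 17.5% to 18.5% gives medians of 2.39 to 2.46 months. Medians from 2.245 to 2.255 months give PFS(6) of 15.7% to 15.8%. The ranges do not meet.

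**Step 3. Reproduce n = 15.**
- Hazard ratio, target to sizing null: 0.1613/0.2858 = 0.564.
- Events, log-hazard form: (1.2816 + 0.8416)²/ln(0.564)² = 13.8.
- Event probability under the target: 1 − [exp(−12 × 0.1613) − exp(−24 × 0.1613)]/(12 × 0.1613) = 0.936.
- Participants: 13.8/0.936 = 14.7, rounded up to 15.

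The one-sample log-rank formula with variance (O+E)/2 gives 14.99, also 15. Two other published-type forms do not give 15: 17.1 with variance E, and 11.6 with a Finkelstein-type form.

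With the 2.25-month null the hazard ratio is 0.1613/0.3081 = 0.523. The two forms that gave 15 now give 11.5 and 11.8, so about 12. The planned 15 therefore comes from the 18% null.

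**Step 4. Operating characteristics.** Simulation used 1,000,000 trials, n = 15, uniform 12-month accrual, 12 months of further follow-up and rejection at z < −1.2816. The readable text does not give the variance form of the test, so three are shown (O = observed events, E = expected events under the null).

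| Truth | Tested against | Variance E | Variance (O+E)/2 | Variance O |
|---|---|---|---|---|
| PFS(6) 18% | 18% | 7.7% | 9.2% | 10.8% |
| PFS(6) 18% | median 2.25 months | 13.4% | 15.6% | 17.8% |
| PFS(6) 38% | 18% | 78.8% | 81.1% | 83.1% |
| PFS(6) 38% | median 2.25 months | 85.7% | 87.4% | 88.9% |
| Median 2.25 months | median 2.25 months | 7.7% | 9.2% | 10.8% |

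**Step 5. Check without simulation.** If all 15 events are observed, total time at risk multiplied by the true hazard follows a gamma distribution with shape 15. Its 90th percentile is 20.13, which is the exact 10% critical value for time multiplied by the null hazard. With the null at 0.3081 and the truth at 0.2858, rejection needs a gamma variate above 20.13 × 0.2858/0.3081 = 18.67, which has probability 16.7%. A normal approximation on the log-hazard scale agrees: 1.2816 − √15 × ln(1.078) = 0.991, giving 16.1%.

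**The case against.** The best reply is that type I error belongs to the null being tested. If the true historical median is 2.25 months, the specified test rejects 7.7% to 10.8% of the time, close to nominal. The fault would then lie only in the sizing, where it is harmless: 15 participants are planned and about 12 would do. The source beside the 18% figure is redacted, and so is the methodology text that opens Protocol 10.1. A non-exponential historical curve could have both a 2.25-month median and an 18% six-month rate, so both numbers may be faithful extracts.

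It can also be said that the medians differ by only about 5 days ((2.43 − 2.25) × 30.4375), that the stated objective is to estimate PFS, and that the Kaplan-Meier curve and its confidence interval do not depend on the null. The figures above ignore the futility look. Treating it as binding brought the rejection rate down from 13.0% to 11.7% in a small run (6,000 trials, variance E, 2.25-month null, truth 18%).

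Much of this is fair, and it limits the claim. The inflation is relative to the 18% benchmark. Use of 2.25 months in the interim simulation is an inference, because no null is named there. But the contradiction survives: the synopsis imposes an exponential on the 18% and Protocol 10.3.1 imposes one on the 2.25 months, so one statement must change. The futility rule is permissive, so it cannot be counted on to restore the error rate, and even as binding it left the rate above 10%. A small gap in medians still moves the rejection rate by 5.7 to 7.0 percentage points.

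**Conclusion.** The concern holds. The Cohort 2 sizing null and test null are different exponentials, in both the protocol and the SAP, and nothing readable in either document reconciles them. If the historical PFS(6) is 18%, the nominal 10% one-sided error becomes 13.4% to 17.8% by variance form (16.7% by the exact gamma calculation), and every form exceeds 10%. The probability of success at the 38% target is overstated by 5.8 to 6.9 points relative to the designed test.

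These figures assume exponential PFS, n = 15, uniform accrual, no dropout and no futility stop; a futility stop could only lower them. If 2.25 months is the intended benchmark, the test keeps roughly its nominal level, and the design null and stated power are what need correcting. The documents do not show which figure the historical source supports.

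**What to change.** State one Cohort 2 null and use it for sizing, the futility simulation and the final test.

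- **If 18% is the benchmark.** This is the natural default, since n = 15, the 10% error and the 80% power all follow from it. In Protocol 10.3.1 and SAP 7.5.2.2, replace the 2.25-month median with PFS(6) equal to 0.18 (hazard 0.286 per month, median 2.43 months). Cohort 3 is already written as a rate in the same table.
- **If 2.25 months is the benchmark.** In the synopsis, Protocol 10.1 and SAP 5, restate the historical PFS(6) as 15.7% and the power at 15 participants as about 86% (variance E; up to 89% with the other forms).

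In either case, name the null in Protocol 10.3.5 and SAP 7.5.4, and name the variance form of the test if the redacted text does not already do so. The choice should be justified from the historical source and fixed before Cohort 2 results are examined.

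The cost is a text change of one number in each affected section. No participants, visits or data are added. Under the first option the test becomes slightly stricter, with power of about 79% to 83%, as designed.

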10.3.2 Safety Analyses

All safety analyses will be performed on the treated population.

Endpoint	Statistical Analysis Methods

Primary
 
Module A and B Safety Lead-in:
 
Incidence of AEs, SAEs, drug-related AEs, AEs leading to discontinuation, and death.
 
AEs will be graded according to CTCAE v4.03.
 
Incidence of laboratory abnormalities
 
Laboratory values will be graded according to CTCAE v4.03.
	
Module A and B Safety Lead-in:
 
Frequency distribution of treated participants with AE using the worst CTC grade. Participants will only be counted (1) once at the preferred term (PT) level, (2) once at the system organ class (SOC) level, and (3) once in the ‘Total participant’ row at their worst CTC grade, regardless of SOC or PT. By Cohort.
 
Lab shift table using the worst CTC grade per participant by Cohort.

Endpoint	Statistical Analysis Methods

Secondary
 
All Cohorts A1-A5, B1-B5:
 
Incidence of AEs, SAEs, drug-related AEs, AEs leading to discontinuation, and death.
 
AEs will be graded according to CTCAE v4.03.
 
Incidence of laboratory abnormalities
 
Laboratory values will be graded according to CTCAE v4.03.
	
All Cohorts A1-A5, B1-B5:
 
Frequency distribution of treated participants with AE using the worst CTC grade. Participants will only be counted (1) once at the preferred term (PT) level, (2) once at the system organ class (SOC) level, and (3) once in the 'Total participant' row at their worst CTC grade, regardless of SOC or PT. By Cohort.
 
Lab shift table using the worst CTC grade per participant by Cohort.

[REDACTED]	[REDACTED]

[REDACTED]

[REDACTED]

[REDACTED]

[REDACTED]

[REDACTED]

[REDACTED]

[REDACTED]

[REDACTED]

[REDACTED]

[REDACTED]

[REDACTED]

